9.3 Criteria for discontinuing participation

The patient can at any time during the course of the study interrupt his / her participation in the study without explaining the reason for this in more detail. The reason why the patient cancels his participation should, if possible, be registered. Data collected up to and including the cessation of study participation will be used in the final analysis of the study.

The examiner may also interrupt the patient's continued participation in the study;

- between the time of inclusion and the administration of study drugs if new data emerges that may pose risks during rituximab treatment, such as the detection of active hepatitis B infection, cancer or other factors that mean that inclusion and exclusion criteria are no longer met.
- after administration of study drugs: as the study involves only one administration of study drugs, continued participation will only be discontinued if the treating physician considers that continued participation in follow-up controls would in any way have negative consequences for the subject's mental or physical well-being. Patients who have been included in the study but have not received study medication before discontinuation of participation, can be replaced with a new participant. Patients who have received study drugs are not substituted by additional participants.

The sponsor reserves the right to terminate the study prematurely based on scientific, administrative and / or ethical reasons. The study may be terminated prematurely if it turns out that the treatment causes a large number of undesirable serious events or if patient recruitment cannot be fulfilled within a reasonable time limit. Decisions on early termination are made by the sponsor / coordinating investigator.

9.4 Screening log

Patients evaluated for possible participation in the study are noted on a screening log at each center. Possible participants are only identified with initials, no personal data may be documented.

9.5 Study personell

The principal investigator at each center is responsible for conducting the study at the center. If study-specific tasks are delegated, it must be documented in writing to which persons and which study-specific tasks have been delegated.

10 Study drug

10.1 Study drug

Mabthera® 500 mg concentrate for infusion, solution

Active substance: Rituximab

ATC-kod: L01XC02

10.2 Description of study drug

Rituximab is a genetically engineered chimeric mouse / human monoclonal antibody consisting of a glycosylated immunoglobulin with human IgG1 constant regions and murine variable regions of the light and heavy chains. The antibody is produced by mammalian (Chinese hamster ovary) cell suspension culture and purified by affinity chromatography and ion exchange, as well as specific viral inactivation and purification steps.

According to the SmPC, Rituximab has been shown to have high specificity for the CD20 antigen on B cells. Toxicity studies in cynomolgus monkeys have not shown any other effects other than the expected pharmacological elimination of B cells in peripheral blood and lymphatic tissue.

Toxicity studies have been performed with cynomolgus monkeys at doses up to 100 mg / kg (treatment on gestational day 20-50) and showed no evidence of fetal toxicity caused by rituximab. In contrast, pharmacologically dose-dependent low levels of B cells in the lymphoid organs were observed in the fetus, which remained postnatally and was followed by a decrease in IgG levels in the newborn animals affected. The number of B cells returned to normal in these animals within 6 months after birth and did not affect the response to vaccination.

Standard tests to examine mutagenicity have not been performed as such tests are not relevant for this molecule. No long-term animal studies have been performed to determine the carcinogenicity of rituximab.

Specific studies to determine the effect of rituximab on fertility have not been performed. In general toxicity studies in cynomolgus monkeys, no adverse effects on male or female reproductive organs were observed.

Protocoll nr: 2015-00887 Date: 2021-04-26

Version 7.0 (ENG) 20(42)

10.3 Placebo

Sodium Chloride, solution for infusion, 9 mg/ml

Active substance: Sodium Chloride

ATC-kod: B05BB01

10.4 Packaging, labeling and handling of study drug

Study drugs (rituximab / placebo) are prepared and labeled at APL.

Mabthera (500 mg / 50 ml vial) is mixed in 250 ml NaCl infusion bags. 50 ml of NaCl is aspirated, 50 ml of Mabthera (500 mg) is added to a strength of 2 mg / ml. For placebo, use 250 ml NaCl in the corresponding infusion bags.

Study drugs are labeled with the date and time of preparation and the date and time of the latest time for use. The maximum shelf life of the study drug is 36 hours according to APL's guidelines.

The study drug is delivered in ready-made infusion bags to the centers during refrigerated transport and temperature log by World Courier. In most cases, delivery will take place within 24 hours.

10.5 Randomization

Study staff at the center contact APL for randomization or contact the study coordinator / study coordinating research nurse at Karolinska for help with randomization via APL.

10.6 Blinding and emergency code breeaking

The study is double-blind and labeling of study drugs (rituximab / placebo) is done by APL.

APL sends a code envelope for the patient in question in connection with sending the study drug to the center. The code envelopes must be stored in a safe place at the center and only opened when information about the given treatment (rituximab / placebo) is deemed necessary for the continued care of the patient. The integrity/status of envelopes will be checked at study center closure.

10.7 Permitted/Not permitted treatments in different study phases

Before screening

I] Permitted: Corticosteroids: Oral - Prednisolone ≤40mg / d within 3 months before screening.

IVIG: Within 12 months before screening

PLEX: Within 12 months before screening

Cholinesterase inhibitors: no restrictions on pre-screening use.

II] Not permitted: Immunosuppressants: Rituximab, azathioprine, cyclosporine, MMF, methotrexate or other immunosuppressants for the treatment of MG. Treatment (excluding rituximab) discontinued> 12 months ago for another indication is permitted

Methylprednisolone pulse

After screening, until randomization

I] Permitted: A stable dose of cholinesterase inhibitor and Prednisolone according to standard schedule if clinically indicated and PLEX and IVIG according to clinical routine.

II] Not permitted: Immunosuppressants: Rituximab, azathioprine, cyclosporine, MMF, methotrexate or other immunosuppressants.

Methylprednisolone pulse

Protocoll nr: 2015-00887 Date: 2021-04-26 Version 7.0 (ENG)

ion 7.0 (ENG) 21(42)

After randomization, until week 8

I] Permitted: Prednisolone: For patients taking Prednisolone, the predetermined schedule of 8 weeks of tapering applies, i.e. 40mg / d, with a reduction of 5mg / v to discontinuation.

Extension of the tapering schedule in clinically clearly unstable patients, but with the aim of

reach a maximum dose of 10mg / day from week 9.

Cholinesterase inhibitors: No restrictions.

IVIG / PLEX: No restrictions.

II] Not permitted: Immunosuppressants: Rituximab, azathioprine, cyclosporine, MMF, methotrexate or other immune suppressants.

Methylprednisolone pulse

After randomization, week 9-24

I] Permitted: Prednisolone: Max dose 10mg / day

Cholinesterase inhibitors: No restrictions.

Immunosuppressants: azathioprine, cyclosporine, MMF or methotrexate may be initiated if clinically

indicated;

Azathioprine: azathioprine, up to 2.5 mg / kg / day divided into one or two doses

Ciclosporin: up to 3mg / kg / day divided into two doses

Methotrexate: up to 20mg / week

II] Not permitted: Immunosuppressants: Rituximab or another immunosuppressant.

IVIG / PLEX

Methylprednisolone pulse

After randomization, week 25-48

I] Permitted: Prednisolone: No restrictions.

Methylprednisolone: No restrictions.

Cholinesterase inhibitors: No restrictions. Immunosuppressants: No restrictions.

10.8 Clinical worsening, rescue treatments

In case of persistent or worsening MG symptoms, rescue treatment should be considered.

Primarily prolonging or reintroducing Prednisolone up to 40mg / d with a new phasing-out schedule; reduction 5mg / week to discontinuation (total treatment time 8 weeks)

Secondarily:

IVIg: total dose 1g / kg, spread over 2-3 days, alternatively

PLEX: A plasma volume is exchanged 3-5 times over 10-14 days

For more info about the above immunomodulatory therapies and the respective degree of evidence at MG, please see the National MG care program at www.snema.se (tab "Documents")

NOTE! Any newly initiated MG immunotherapy (excluding azathioprine, methotrexate and ciclosporin) or dose increase of Prednisolone> 10 mg / d during weeks 9-24 will by definition be considered rescue treatment. This also includes rituximab.

Protocoll nr: 2015-00887 Date: 2021-04-26

Version 7.0 (ENG) 22(42)

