6.1 Primary question

Is rituximab more effective than placebo at achieving minimal clinical MG symptoms without the need for higher doses of oral corticosteroids or rescue treatments at 16 weeks post-treatment?

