7.1 Primary endpoint

Proportion of patients with QMG score \leq 4 and a daily dose of Prednisolone of \leq 10mg and no rescue treatment at 16 weeks after study start

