Starting dose 40 mg / day, with tapering of 5 mg / week until discontinuation.

For patients already on Prednisolone before screening, the pre-screening dose may be increased to 40 mg / day with subsequent tapering according to the above schedule.

To reduce the risk of study endpoints being affected by another MG-specific treatment, such treatment should be given after randomization in accordance with section 10.7, Permitted / non-permitted treatment at different times.

If the cortisone dose can not be reduced due to persistent or worsening clinical symptoms, you may first choose to increase the dose of Prednisolone and make a new plan for phasing out or, secondly, to give rescue treatment with IvIg or PLEX.

Immunosuppressive therapy (azathioprine, ciclosporin, MMF, methotrexate) can be started if indicated from 12 weeks after randomization. Pulse cures with cortisone should not be given after randomization. In cases where the study physician for medical reasons considers that the above treatments are insufficient or inappropriate, other treatment may also be considered, including rituximab. The patient will then be classified as a non-responder in the primary outcome measure and censored in the secondary outcome measures.

Protocoll nr: 2015-00887 Date: 2021-04-26 Version 7.0 (ENG)

7.0 (ENG) 16(42)

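### The 10.8 NOTE that defines rescue for the primary endpoint does not match the permitted-treatment rules for MMF, and does not clearly cover prednisolone above 10 mg/d carried over from before week 9

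*Combined protocol and SAP*

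**What the plan says.** Section 7.1 defines response as QMG of 4 or less, prednisolone of 10 mg/d or less, and "no rescue treatment at 16 weeks after study start". The primary question in 6.1 asks for response "without the need for higher doses of oral corticosteroids or rescue treatments".

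The only text that defines rescue outright is the NOTE in 10.8, which covers "Any newly initiated MG immunotherapy (excluding azathioprine, methotrexate and ciclosporin) or dose increase of Prednisolone> 10 mg / d during weeks 9-24". Other sections bear on the same patients:

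- **10.8, opening text.** The first rescue step is "Primarily prolonging or reintroducing Prednisolone up to 40mg / d with a new phasing-out schedule"; IVIG or PLEX comes second. No week limit is given.
- **8.4, steroids.** If the dose cannot be reduced, "you may first choose to increase the dose of Prednisolone and make a new plan for phasing out or, secondly, to give rescue treatment". The rescue meant here is IVIG or PLEX.
- **8.4, immunosuppressants.** "Immunosuppressive therapy (azathioprine, ciclosporin, MMF, methotrexate) can be started if indicated from 12 weeks after randomization". Other treatment, including rituximab, may be used if these options are inadequate, and the patient is then a non-responder.
- **10.7, to week 8.** Permitted: "Extension of the tapering schedule in clinically clearly unstable patients, but with the aim of" a maximum of 10 mg/d from week 9. IVIG and PLEX are unrestricted in this period.
- **10.7, weeks 9-24.** "I] Permitted: Prednisolone: Max dose 10mg / day". Azathioprine, ciclosporin, MMF and methotrexate may be started. Oral prednisolone above 10 mg/d is not in the not-permitted list.
- **13.2.** Patients given treatment that 10.7 does not allow, between randomization and the week-16 visit, are non-responders.

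**The concern.** Rescue is one of three components of the primary endpoint, so its definition has to give one clear answer for every patient. Two groups do not get one that fits the rest of the plan.

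A patient who starts MMF between week 9 and the week-16 visit is treated as 10.7 allows (or as 8.4 allows, from week 12), yet fails under the NOTE. A patient given azathioprine in the same circumstances does not fail. The plan gives no reason for the difference.

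A patient whose prednisolone was raised or prolonged before week 9, and who is still above 10 mg/d after week 9 begins, has needed the higher steroid doses that the primary question means to exclude. The NOTE speaks of an increase within weeks 9-24, so a dose carried over is not clearly rescue. If the taper has finished by the visit and QMG is 4 or less, responder status turns on how 13.2 is read.

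The study has 47 patients, and only those who otherwise meet the QMG and dose criteria are affected. A few such patients could change the p-value noticeably, and a coding choice of this kind should not be made with treatment codes known.

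**Working it through.** **1. MMF, sections side by side**

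| Started before the week-16 visit | 10.7, weeks 9-24 | 8.4, from week 12 | 10.8 NOTE |
|---|---|---|---|
| Azathioprine, ciclosporin or methotrexate | permitted | permitted | exempt, not rescue |
| MMF | permitted | permitted | not exempt, so rescue; fails 7.1 |

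Section 13.2 does not fail MMF, because 10.7 permits it. Section 8.4 attaches non-responder status to treatments beyond its own list, and MMF is on that list.

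**2. Prednisolone carried past week 8**

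Inputs: the 10.8 taper (40 mg, down 5 mg each week); infusion = day 0; week 9 taken to start on day 57; week-16 visit on day 112, with the 21-day window of 8.5 allowing day 91.

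Dose on day t after a restart on day s = max(0, 40 - 5 × floor((t - s)/7)).

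Example, s = 43: on day 57, (57 - 43)/7 = 2, so 40 - 10 = 30 mg. The dose first reaches 10 mg when t - s = 42, on day 85.

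| Restart day | Dose, day 57 | Days above 10 mg from day 57 | Dose, day 91 | Dose, day 112 |
|---|---|---|---|---|
| 15 | 10 mg | 0 | 0 mg | 0 mg |
| 16 | 15 mg | 1 | 0 mg | 0 mg |
| 29 | 20 mg | 14 | 0 mg | 0 mg |
| 43 | 30 mg | 28 (days 57-84) | 10 mg | 0 mg |
| 49 | 35 mg | 34 | 10 mg | 0 mg |
| 50 | 35 mg | 35 | 15 mg | 0 mg |
| 56 | 40 mg | 41 (days 57-97) | 15 mg | 0 mg |

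All 41 restart days from 16 to 56 give 0 mg on day 112. Restarts on days 50-56 are at 15 mg on day 91, so a visit that early would catch them through the dose criterion.

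**3. Effect on the primary test (illustration)**

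Assumed: a 24/23 split of N = 47, and 19/24 rituximab vs 9/23 placebo responders, close to the planned 80% and 40%. Two-sided Fisher's exact test, with carried-over patients recoded from responder to failure:

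| Recoded to failure | Rituximab vs placebo | p |
|---|---|---|
| none | 19/24 vs 9/23 | 0.008 |
| 2 placebo | 19/24 vs 7/23 | 0.001 |
| 2 in each arm | 17/24 vs 7/23 | 0.009 |
| 2 rituximab | 17/24 vs 9/23 | 0.042 |
| 3 rituximab, 1 placebo | 16/24 vs 8/23 | 0.042 |
| 3 rituximab | 16/24 vs 9/23 | 0.082 |

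Exempting MMF moves patients the other way, from failure to responder. From the same start, one, two or three added placebo responders give p = 0.017, 0.036 and 0.069.

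**4. Power if carried-over doses count as failure**

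The revised power figures in 13.1 (81%, 85% and 89% at 20, 22.5 and 25 per arm) are reproduced by the unpooled normal approximation: 0.807, 0.851 and 0.885. The planned test is Fisher's exact test, so its exact power at 24/23 is the baseline here: 0.80 for 80% vs 40%. Assumed shares of would-be responders recoded:

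- 10% in both arms (72% vs 36%): 0.69
- 20% in both arms (64% vs 32%): 0.57
- 10% in rituximab only (72% vs 40%): 0.58
- 10% in placebo only (80% vs 36%): 0.87

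**The case against.** A reader might infer that 8.4, 10.7, 10.8 and 13.2 give the same patient opposite scores. The documents do not support that. Section 10.7 says what may be given, not how it is scored. Section 13.2 does not say that only disallowed treatment makes a non-responder, so a drug can be permitted and still count as rescue. The order in 8.4, prednisolone first and then IVIG or PLEX, is the same as in 10.8, and 8.4 never states that a prednisolone increase is not rescue. The opening of 10.8 cannot safely be taken as the scoring rule either: it lists IVIG and PLEX with no week limit, although 10.7 leaves them unrestricted to week 8. Finally, exceeding a stated maximum can reasonably be read as not allowed, which would make the carried-over patient a non-responder under 13.2.

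All of this stands, and it reduces the point from contradiction across the plan to a mismatch between the NOTE and the rest. It does not remove the mismatch. Reading permitted and rescue as compatible gives MMF one score, but still separates it without explanation from the three drugs listed beside it. Reading the 10 mg maximum as a prohibition settles the carried-over dose, but 10.7 puts that maximum under permitted treatment, makes it only an aim when the taper is extended, and leaves higher oral doses out of the not-permitted list.

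It is also fair to say that patients ill enough to need MMF or a prolonged course may seldom reach QMG of 4 or less by week 16. The documents give no figure for this.

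**Conclusion.** The concern holds in a limited form and is minor. Applied as written, the NOTE fails a patient who starts MMF that 10.7 and 8.4 permit, and it does not clearly count a prednisolone dose above 10 mg/d carried over from before week 9. The dose criterion at a day-112 visit does not catch such a course for restarts on days 16-56.

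The size is unknown, because the documents do not say how many patients fall in either group or in which arm. It might be inferred that recoding any two patients could overturn the result. In the illustration no recoding of two does so: the smallest change to failure that crosses 0.05 is three rituximab responders with no placebo responder, and in the MMF direction it is three added placebo responders with none in rituximab. These figures rest on the assumed 24/23 split and on responder counts near the planned rates; the day counts rest on the 10.8 taper being followed exactly.

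The week-24 responder endpoint in 7.3 uses the same rescue component and has the same two gaps.

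**What to change.** Before unblinding:

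1. Add MMF to the exceptions in the 10.8 NOTE, which brings it into line with 10.7 and 8.4. If MMF was meant to count as rescue, say so in both of those sections instead.
2. State in 13.2 whether prednisolone above 10 mg/d at any time from week 9 to the week-16 visit, including a dose carried over from before week 9, is non-response. The suggested answer is yes, in line with the 10.7 maximum and the primary question. Report the primary Fisher test under the other coding as well.
3. Use the same wording, up to the week-24 visit, for the responder endpoint in 7.3.

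If the data are already unblinded, do not choose between codings; report the primary test under both for each group.

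The drafting cost is one edit and one sentence. No new data are needed, since medication and prednisolone dose are already checked at weeks 2, 4, 8, 12 and 16. The real cost is that item 2 fails some patients whose longer taper 10.7 allowed, and it may lower power: from 0.80 to 0.69 if 10% of would-be responders in both arms are recoded. Power rises if the recoded patients are mainly on placebo.

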10.9 Study drug documentation, accountability

The investigator is responsible for the study drugs that are received, administered, or destroyed at the center being registered on the intended documents by delegated staff.

When administering study drugs, this is documented with information such as who gave the drug, patient, date, and time.

10.10 Treatment after study end

After the end of the study, the patient will be treated according to a clinical assessment by the treating physician.

11 Assessement of safety and efficacy

11.1 Blood samples

Blood samples for analysis of CBC including diff., Na, K, Creatinine, Asat, Alat, CRP, Glucose, hepatitis B screening and total IgG are taken at screening and analyzed at the local laboratory at each hospital.

Blood samples for analysis of drug antibodies and markers of disease activity, such as acetylcholine receptor antibodies, are taken in the study for evaluation of tertiary issue / exploratory analyzes in the study.

Analysis of autoantibodies is performed at Clinical Immunology / Transfusion Medicine, Karolinska University Laboratory after completion of the study.

Antibody antibodies and samples for exploratory analyzes will be sent to the Center for Molecular Medicine (CMM) at Karolinska Institutet (KI).

In total, a blood volume of about 50 ml is drawn from the patient during the study.

11.2 Quantitative Myastenia Gravis scale, QMG

The QMG scale is used in the study to evaluate primary, secondary, and tertiary study objectives.

The scale is used for quantitative evaluation of MG status and will be carried out by testers who have not participated in the administration of the study drug. The scale consists of 13 domains that are scored 0-3 as well as information about MGFA and subjective health status.

Evaluations on the scale take about 20-30 minutes to complete and are carried out during visits to the center.

11.3 Myasthenia gravis activities of daily life scale, MG-ADL

The MG-ADL scale is used in the study to evaluate secondary and tertiary study objectives.

The scale consists of eight items such as speech, swallowing, double vision, and mobility where the patient himself estimates activities in daily life on a three-point scale.

Filling in the form takes about 5 -10 minutes and is carried out by the patient during a visit to the center together with the research nurse.

11.4 EuroQol 5-dimensions quality of life, EQ5D

The EQ5D health survey is used in the study to evaluate tertiary study objectives.

EQ5D is an instrument for measuring health and has been developed by EuroQol Group. The form contains a part with 5 items where the patient classifies his health, such as mobility, main activities, pain / discomfort, and a part with a scale where the patient estimates his current state of health based on the criteria best to worst imaginable.

Filling in the form takes about 5 -10 minutes and is carried out by the patient during a visit to the center together with the research nurse.

Protocoll nr: 2015-00887 Date: 2021-04-26 Version 7.0 (ENG)

on 7.0 (ENG) 23(42)

11.5 Quality of life in myasthenia gravis, MG-QOL15

MG-QOL15 is used in the study for evaluation of secondary and tertiary study objectives.

MG-QOL15 is a short form for evaluation for certain aspects of quality of life associated with myasthenia gravis.

The form consists of 15 items, such as frustration over the condition, difficulty eating, difficulty speaking, difficulty walking, etc. The patient himself estimates his function on a five-point scale based on criteria from not at all to very much based on how the statements are true during the last 4 weeks.

Filling in the form takes about 5 -10 minutes and is carried out by the patient during a visit to the center together with the research nurse.

